The study methodology will be similar to a previous companion pan-European survey, conducted in 18 European countries in 2010 within an EU Seventh Framework Programme (FP7) Project, entitled “Pricing Policies And Control of Tobacco in Europe” (PPACTE; Grant Agreement HEALTH-F2-2009-223323) [21]. Briefly, in each country, the study sample will be representative of the general population aged 15 years and over in terms of age, sex, geographic area, and socio-economic characteristics. The multi-stage methodology will be used as the preferred sampling methodology. In the first stage, the primary unit of selection will be geographic area or voting centre. In the second stage, households or municipalities will be selected. In the last stage,

respondents will be chosen randomly, in order to be representative of the population. In those countries where adult respondents will be selected from electoral rolls, the quota method will be used to select minors (i.e., aged 15 to 17). Other methods, including stratified or simple sampling or quota methods, will also be accepted wherever it is not possible to conduct a multistage random sampling.

Selection of countries

For the present study, an appropriate sample of 12 European countries – all EU Member States (MS) – representing geographical, legislative and cultural variations across the EU, has been selected.

The selected European countries are the following: Bulgaria (BG), England (UK), France (FR), Germany (DE), Greece (GR), Ireland (IE), Italy (IT), Latvia (LV), Poland (PL), Portugal (PT), Romania (RO), and Spain (ES).

These countries were selected after taking into account several aspects, including: i) different geographical distribution; ii) different level of per capita income; iii) different national smoking prevalence [21]; iv) different adoption of tobacco control strategies at a national level (i.e., Tobacco Control Scale, TCS) [22]; v) different tobacco ban legislations [22]; vi) high population size; vii) inclusion in a previous PPACTE survey [21].

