According to geographic area, we considered countries from northern (IE, UK), central/western (DE, FR), central/eastern (BG, LV, PL, RO), and southern Europe (ES, IT, GR, PT). Moreover, the selection includes the 7 most populated EU MS (DE, ES, FR, IT, UK, PL, RO), and, among less populated countries, we prioritized middle-income countries (BG, RO). Finally, besides Germany, all the other countries were included in the 2010 PPACTE survey. Overall, the 12 selected EU MS represent 78.8% of the EU28 overall population.

Study population

In each of the 12 selected European countries, approximately 1000 individuals, representative of the general population aged 15 years and over in terms of age, sex, geographic area, and socio-economic characteristics, will be enrolled in this cross-sectional study. The final sample will therefore include a total of approximately 12,000 subjects.

Inclusion criteria

- individuals aged 15 years and over;
- individuals resident of the 12 selected countries;
- individuals able to understand and answer the questions of the questionnaire of the study in the country-specific language;
- individuals who formally accept to participate in the study.

Exclusion criteria

No specific exclusion criteria are considered.

Sample size computation

The sample size in each specific country will allow us to obtain prevalence estimates with a maximum standard error (SE) lower than $\pm 1.6\%$. Therefore, with such a sample size we will be able to provide stable prevalence estimates (with a relatively small 95% confidence interval), overall but also in each specific country.

Data collection

In each country, individuals will be surveyed by trained interviewers through face-to-face interviews using a structured standardized questionnaire. Data collection will be coordinated by DOXA, a leading market research organization and Italian branch of the Worldwide Independent Network/Gallup International Association (WIN/GIA), and performed in collaboration with its

European partners (see “Selection of the subcontractor performing data collection” paragraph). Whenever possible, data will be collected within computer assisted personal interviews (CAPI). Alternatively, paper and pencil (P&P) interviews will be accepted. Data collection will start once obtained the approval from the Ethics Committee of the 12 European countries involved in the study. The fieldworks will last two to three months in each country.

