This task is included in the WP3 of the TackSHS Project. Once the fieldwork is completed, DOXA will collect data from its European partners, and, after internal checks, will provide to “Mario Negri” Institute, the 12 anonymous data files in text format, with the corresponding codebook in English language. The 12 data files will be managed by the expert biostatisticians at the Department of Epidemiology of “Mario Negri” Institute. Through the use of the statistical package SAS, version 9.4 (SAS Institute, Cary, NC, USA), they will perform the input of the 12 textual data file into 12 corresponding SAS datasets, and then create a unique final dataset SAS. This dataset will be checked for coherence and for the presence of possible errors, cleaned, and finalized through the generation of queries which will be addressed by DOXA and its European partners.

Statistical analyses for WP3

Statistical analyses required to achieve objectives related to WP3 will be conducted by expert biostatisticians at the Department of Epidemiology of “Mario Negri” Institute, using SAS statistical package.

Prevalence of current smokers and e-cigarette users, and prevalence of exposure to SHS and e-cigarette aerosol, will be estimated through univariate statistical analyses (i.e., descriptive statistics for categorical data, including absolute or relative frequencies), overall, by country, and in strata of selected demographic and socio-economic (individual and country-specific) characteristics.

Continuous variables (e.g., age at starting or quitting smoking, number of cigarettes smoked per day, number of e-cigarette puffs per day) will be summarized through the use of means and standard deviations. Alternatively, they will be categorized, and thus described through absolute or relative frequencies.

Multivariate analyses will also be considered to identify sub-groups of the population (e.g., young vs. other age groups, unemployed vs. other working status, low vs. high educated subjects) or clusters of countries (e.g., middle vs. high income countries, low vs. high TCS, low vs. high smoking prevalence) more frequently adopting selected tobacco-related behaviours or more frequently exposed to SHS. Thus, odds ratios (OR), and the corresponding 95% confidence intervals (CI), will be estimated through logistic regression models after adjustment for age, sex, socio-economic status, and other selected individual-level characteristics. Multi-level procedures will also be considered.

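### Household, electoral-roll and quota samples are all analysed with plain unweighted frequencies, so home SHS prevalence may be biased, probably downward, in countries that interview one person per household

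*Combined protocol and SAP*

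**What the plan says.** Under Study design, multi-stage sampling is preferred. The first stage is a geographic area or voting centre. For the next stage, "In the second stage, households or municipalities will be selected". At the last stage, "respondents will be chosen randomly, in order to be representative of the population". Two further routes are allowed. "In those countries where adult respondents will be selected from electoral rolls, the quota method will be used to select minors", meaning ages 15 to 17. And "Other methods, including stratified or simple sampling or quota methods, will also be accepted wherever it is not possible to conduct a multistage random sampling".

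The section does not say which country uses which route, how households are drawn, or how many people are interviewed in each.

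Study population promises a sample "representative of the general population aged 15 years and over in terms of age, sex, geographic area, and socio-economic characteristics". Household size is not one of those dimensions.

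In Statistical analyses for WP3, the prevalences of smoking, e-cigarette use and passive exposure "will be estimated through univariate statistical analyses (i.e., descriptive statistics for categorical data, including absolute or relative frequencies"), overall, by country and in strata. Design weights and post-stratification weights are not mentioned there or elsewhere.

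On precision, "The sample size in each specific country will allow us to obtain prevalence estimates with a maximum standard error (SE) lower than" 1.6%, with about 1000 people per country.

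**The concern.** A plain frequency estimates a person-level prevalence only if every person has the same chance of selection. A roll sample of adults can meet that condition. A household sample with one respondent per household does not: a person living alone is certain to be chosen once the household is drawn, whereas a person in a household with four eligible residents has one chance in four. The plain frequency is then an average over households, not over people.

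This matters most for exposure at home, which the questionnaire measures. A person living alone has no co-resident smoker, so home exposure can be expected to rise with the number of residents. Under-representing larger households would then pull the estimate down.

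Comparing SHS exposure between middle- and high-income countries is a stated objective. If some countries sample households and others sample persons, part of a difference could come from the route. Survey prevalences also feed the attributable-burden work (WP9) and the economic model (WP10).

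**Working it through.** **1. The plan's own figure.** With n = 1000 and p = 0.5, SE = sqrt(0.25/1000) = 1.58%, which is below 1.6%. The figure reproduces, but only for simple random sampling with equal weights.

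**2. Formulas.** Assume that households are drawn with equal probability and that one eligible resident is chosen at random in each. Let h_k be the share of households with k residents aged 15+, and e_k the home SHS prevalence among their members. A person's inclusion probability is proportional to 1/k.

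- Unweighted estimate: U = Σ h_k e_k
- Person-level prevalence: T = Σ k h_k e_k / Σ k h_k
- Bias: U − T

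**3. Inputs.** The documents give neither h_k nor e_k, so all values here are assumptions, with households of four or more treated as k = 4. Household shares for k = 1/2/3/4:

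- Mix A: 35/45/13/7%, mean 1.92
- Mix B: 25/45/18/12%, mean 2.17
- Mix C: 20/40/22/18%, mean 2.38

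**4. Mix B in full.**

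- Steep gradient, e = 8/18/26/32%. U = 0.25×8 + 0.45×18 + 0.18×26 + 0.12×32 = 18.62%. T = (0.25×8 + 0.90×18 + 0.54×26 + 0.48×32)/2.17 = 47.60/2.17 = 21.94%. Bias -3.32 points.
- Mild gradient, e = 15/18/21/24%. U = 18.51%. T = 42.81/2.17 = 19.73%. Bias -1.22 points.

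**5. All mixes (bias in percentage points).**

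| Assumed home exposure, k = 1/2/3/4 | Mix A | Mix B | Mix C |
|---|---|---|---|
| Steep rise, 8/18/26/32% | -3.32 | -3.32 | -3.33 |
| Mild rise, 15/18/21/24% | -1.18 | -1.22 | -1.25 |
| Flat, 20% | 0 | 0 | 0 |
| Mild fall, 24/21/18/15% | +1.18 | +1.22 | +1.25 |

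A more extreme model, in which each other eligible resident independently exposes the respondent with probability 0.15 and people living alone are never exposed, gives -5.2 to -5.4 points.

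**6. Against sampling error.** At U near 18.6% and n = 1000, SE = sqrt(0.186×0.814/1000) = 1.23 points. The mild bias is about one SE and the steep bias about 2.7 SEs. Neither shrinks as n grows.

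**7. Any-site exposure.** If a share s is exposed elsewhere, independently of household size and of home exposure, any-site prevalence is s + (1 − s) × home prevalence, so the bias is multiplied by (1 − s). With s = 0.5 (assumed), Mix B gives -1.7 (steep) and -0.6 (mild).

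**8. Cost of weighting by k.** Kish design effect = Σ k² h_k / (Σ k h_k)².

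- Mix A: 4.44/3.686 = 1.204, maximum SE 1.58% × sqrt(1.204) = 1.74%
- Mix B: 5.59/4.709 = 1.187, maximum SE 1.72%
- Mix C: 6.66/5.664 = 1.176, maximum SE 1.71%

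Keeping 1.6% would need n = 0.25 × deff/0.016², about 1150 to 1180 per country. Clustering by area is not included.

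**9. Is the trade worthwhile?** In Mix B with the mild gradient, unweighted root mean squared error is sqrt(1.22² + 1.23²) = 1.73 points. The weighted SE is sqrt(0.197×0.803/1000) × sqrt(1.187) = 1.37 points. Weighting has the smaller total error even with the mild gradient. If exposure is flat it only adds variance: 1.26 becomes 1.38 points.

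**The case against.** The strongest reply is that the mechanism is inferred. The plan states neither equal-probability household selection nor one respondent per household, and it assigns no country to the household route. If every eligible resident were interviewed, or households were drawn in proportion to size, this bias would vanish. That stands, and it is why the point is conditional. It does not remove the need to specify the route, because interviewing whole households would bring within-household clustering that plain frequencies also ignore.

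Other replies have partial force:

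- Balance on age, sex, area and socio-economic characteristics could remove some of the bias. Household size still varies within those groups, and no calibration is described.
- The sampling method is already to be recorded for each country. That comes close to listing the route, but it does not supply weights.
- The demographic items are given only as examples and the questionnaire annex is not in the documents. It cannot be said that household size is not asked.

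A reader might infer that home SHS is definitely understated, by several points, in identifiable countries, and that the country comparisons and the WP9 and WP10 results are therefore wrong. The documents do not support this. They give no household-size mix and no exposure by household size. The direction rests on a plausible rising gradient, since a flat one gives zero and a falling one reverses the sign. The arithmetic concerns home exposure, one of several sites measured, and no effect on WP9 or WP10 output has been shown.

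**Conclusion.** The point holds conditionally. The plan permits routes with different selection probabilities, analyses them all with the same unweighted estimator, and has no design weight. In any country that draws households with equal probability and interviews one resident, larger households are under-represented. Home SHS prevalence there may be biased, probably downward, and contrasts with roll-sampled countries may partly reflect recruitment.

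The size is unknown from the documents. Under the three assumed mixes it is about -1 point for a mild rising gradient and about -3 for a steep one, and zero if exposure does not depend on household size. Any-site exposure would be less affected. The plan should be changed before fieldwork, because the eligible count may be hard to recover afterwards, once identifiers have been deleted.

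**What to change.** **Study design.** State how households are drawn and how many respondents are taken in each. In household-sampled countries, have the interviewer record the number of eligible residents aged 15+ at selection.

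**Statistical analyses for WP3.**

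- Household samples with one respondent: estimate prevalences and ORs with a design weight proportional to the eligible count, trimmed at a limit fixed in advance, then calibrated to the country's age, sex and area distribution so that the promised balance is kept.
- Person-list samples: household-size weight of 1.
- Quota samples, and minors selected by quota in electoral-roll countries: calibration only, because their selection probabilities are unknown.
- Report the selection route by country beside the results.

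**2010 comparison.** The plan relies on the same country-specific sampling in both surveys. Leave both unweighted unless the 2010 data hold household size, in which case weight both.

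**Sample size computation.** Restate the maximum SE as about 1.7 to 1.75% in household-sampled countries, noting that this allows for weighting only and rests on assumed household mixes.

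**Cost.** One item at selection, a weighting paragraph, a table of routes, and population margins for calibration. The statistical price is the design effect of about 1.2. Offsetting it would take roughly 150 to 180 more interviews per household-sampled country, so restating the precision is the cheaper choice.

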The English version of the questionnaire (Annex 4) has been developed through the collaboration with the partners of the TackSHS consortium. Before fieldwork, DOXA and its European partners will translate the questionnaire, under the supervision of the TackSHS consortium, in various country-specific languages. Some questions are identical to those formulated in a previously conducted pan-European survey (the PPACTE survey), in order to allow comparisons in time.

The first part of the questionnaire includes country-specific data to be provided by DOXA and its European partners for each European country. These data include i) information on sampling methodology (e.g., sampling method used, response rate, fieldwork dates, age range), and ii) country-specific information (e.g., country population size, price of cigarette packs, gross domestic product, structure of the school system, and current policies regulating tobacco smoking and electronic cigarette use implemented at a national level, with a focus on indoor public/private places and transports, and outdoor public places).

The second part of the questionnaire is designed to collect individual-level information for each survey participant, and is divided in four sections:

- A. socio-economic and demographic characteristics (e.g., sex, age, level of education, and profession);
- B. cigarette smoking habit and e-cigarette use (e.g., smoking status, use of e-cigarette –and, in Italy, use of heat-not-burn tobacco cigarette-, smoking/vaping intensity and duration, and consequences of e-cigarette use on smoking behaviour);
- C. cigarette smoking, e-cigarette consumption, and SHS and e-cigarette aerosol exposures in different sites (e.g., exposure to SHS in indoor public places, workplaces, private venues, also in presence of minors, homes, transports, and selected outdoor places);
- D. attitudes and perceptions on smoke-free regulations and awareness of SHS harmful effects.

Statistical analysis plan

Creation of the survey dataset

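### The per-country maximum SE of 1.6% holds only for simple random sampling; the preferred multistage design is not allowed for

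*Combined protocol and SAP*

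**What the plan says.** Study population sets about 1000 respondents in each of 12 countries. Sample size computation then states: "The sample size in each specific country will allow us to obtain prevalence estimates with a maximum standard error (SE) lower than" 1.6%. It concludes that "we will be able to provide stable prevalence estimates (with a relatively small 95% confidence interval), overall but also in each specific country". It gives no formula, prevalence, design effect, intraclass correlation (ICC) or allowance for weighting.

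Study design describes how respondents are found: "The multi-stage methodology will be used as the preferred sampling methodology". It adds: "In the first stage, the primary unit of selection will be geographic area or voting centre". Households or municipalities come next, then respondents. As a fallback where multistage sampling is not possible, "Other methods, including stratified or simple sampling or quota methods, will also be accepted".

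The country-level items listed under Data collection include "information on sampling methodology (e.g., sampling method used, response rate, fieldwork dates, age range"; the examples mention no number or size of primary units and no weight. Under Statistical analyses for WP3, prevalences "will be estimated through univariate statistical analyses (i.e., descriptive statistics for categorical data, including absolute or relative frequencies), overall, by country". The only method there that could address clustering comes at the end of the odds-ratio paragraph: "Multi-level procedures will also be considered".

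**The concern.** A bound called a maximum and applied to each country has to hold at the least favourable prevalence, 50%, and under the sampling design that will actually be used. The figure matches a simple random sample, which the plan accepts only as a fallback. Respondents from the same area or voting centre tend to resemble one another in smoking and in secondhand smoke (SHS) exposure, which raises the variance above the simple-random value unless stratification offsets it.

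This is the plan's only precision justification, and the promise of stable country estimates rests on it. The prevalence at which the bound is tightest is a realistic one: Background and rationale cites SHS exposure of 20% to 60% among European non-smokers. If the published intervals make the same simplification, they will be too narrow. Statistical analyses for WP10 takes SHS exposure for Germany, Spain and the UK from this survey and requires confidence intervals for model parameters, so understated uncertainty could pass into those sensitivity analyses.

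**Working it through.** **Inputs from the plan:** n = 1000 per country (approximate); maximum SE 1.6%; 95% intervals; multistage sampling preferred. **Assumed, because the documents give none:** design effect (DEFF), respondents per primary unit (m) and ICC.

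**1. The plan's figure.** SE = sqrt(p(1 − p)/n), largest at p = 0.5: sqrt(0.25/1000) = 0.01581, or 1.58%. This reproduces the stated bound. That the plan used simple random sampling at p = 0.5 is inferred from this match. The smallest n that meets 1.6% on this basis is 0.25/0.016² = 976.6, so 977. At n = 950 the SE is already 1.62%.

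**2. Room for a design effect.** Maximum DEFF = 0.016² × 1000 / (p(1 − p)):

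| Prevalence | Maximum DEFF |
|---|---|
| 50% | 1.024 |
| 30% | 1.22 |
| 20% | 1.60 |
| 6.8% (ever e-cigarette use in Italy, Background and rationale) | about 4.0 |

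**3. What that means for clustering.** With DEFF = 1 + (m − 1) × ICC and p = 0.5, the largest tolerated ICC is 0.024/(m − 1). This gives 0.006 for m = 5, 0.0027 for m = 10 and 0.0013 for m = 20.

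**4. Precision under assumed design effects.** SE = sqrt(0.25 × DEFF/1000) at p = 0.5; half-width = 1.96 × SE; effective n = 1000/DEFF. The 1.6% bound fails where p(1 − p) > 0.256/DEFF. Coverage of a nominal 95% interval that ignores DEFF is 2Φ(1.96/√DEFF) − 1.

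| DEFF | SE | Half-width (points) | Effective n | Prevalences where 1.6% fails | Coverage if ignored |
|---|---|---|---|---|---|
| 1.0 | 1.58% | 3.1 | 1000 | none | 95% |
| 1.25 | 1.77% | 3.5 | 800 | about 29–71% | 92% |
| 1.5 | 1.94% | 3.8 | 667 | about 22–78% | 89% |
| 2.0 | 2.24% | 4.4 | 500 | about 15–85% | 83% |

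**5. Pooled estimate.** With 12,000 respondents, sqrt(0.25/12000) = 0.46%, and 0.016²/(0.25/12000) = 12.3. The pooled sample has ample room at this bound; the problem is in the country estimates.

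**The case against.** The strongest reply is that no figure is wrong. The SE was computed correctly and rounded up, and the limit of 1.024 largely reflects the gap between 1.58 and 1.6: a stated bound of 2% would have tolerated 0.02² × 1000/0.25 = 1.6. A DEFF of 1.1 gives 1.66%, which matters little. This is fair, and 1.024 should not be read as a threshold for harm. It does show that the figure contains no allowance for the preferred design.

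Next, no breach is demonstrated. Every DEFF above is an assumption, stratification could offset clustering, and the documents do not say which country uses which method. Simple or proportionately stratified unclustered samples of at least 977 would meet the bound, and low-prevalence items are safe under much larger design effects. All of this stands. The finding is that the maximum is unsupported, not that every country exceeds it.

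Third, the sampling items are given as examples, the questionnaire annex is not in the text, and the 2010 survey's methods are cited rather than reproduced, so primary-unit detail may exist elsewhere. That is possible, but it would not put a design effect into the precision statement or a variance method into the analysis plan.

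Finally, the plan names no interval method for prevalence, so the coverage losses and the effect on WP10 are conditional. They are: they apply only if the intervals ignore clustering, as the bound does.

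**Conclusion.** The concern holds. The 1.6% figure is right for a simple random sample of 1000 at 50% prevalence, and wrong as an unconditional maximum for a survey whose preferred design is multistage. In clustered countries it holds at mid-range prevalences only if clustering is negligible or offset by stratification. For quota samples it has no design-based support at all.

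If the design effect were between 1.25 and 2.0, the worst-case half-width would be 3.5 to 4.4 points instead of 3.1. That is still usable precision, so the survey's size is not in question. What needs correcting is the stated precision and the absence of a variance method that fits the design. Confidence is high that the condition is missing. The size of the effect in any one country cannot be known from the documents.

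**What to change.** 1. **Sample size computation:** restate the bound as maximum SE = sqrt(0.25 × DEFF/n), naming the prevalence, n and assumed DEFF; for example, 1.6% to 2.2% for assumed DEFF from 1.0 to 2.0. The range is illustrative and should be labelled as an assumption.
2. **Data collection:** add the number of primary units and the respondents per unit to the country sampling information.
3. **Creation of the survey dataset and Statistical analyses for WP3:** have each data file carry a coded, non-identifying primary-unit identifier and a weight. Where sampling is multistage, compute country prevalence intervals with design-based variance using both. Label intervals from quota samples as model-based.
4. **Statistical analyses for WP10:** use these intervals in the sensitivity analyses.

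The cost is a few sentences, two variables per file and a little more analysis, with no added recruitment. The stated precision becomes less favourable, and intervals will probably widen in clustered countries. The unit code needs care: the plan promises anonymous files, and an area code beside age, sex and profession could raise the risk of re-identification. The variables should be requested before the files are delivered, because Privacy observance procedures has the encryption key destroyed after quality assurance and the link to primary units may not be recoverable afterwards.

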- WP3, coordinated by “Mario Negri” Institute (Milan, Italy): Survey on secondhand smoke and electronic cigarettes in Europe;
- WP9, coordinated by ISPO (Florence, Italy): Attributable mortality and morbidity to secondhand smoke in Europe;
- WP10, coordinated by Universidad Politécnica de Cartagena (Cartagena, Spain): Economic impact of secondhand tobacco smoke on morbidity and mortality and Return on Investment of Intervention.

Objectives of this cross-sectional study are:

- to estimate prevalence of current smokers, electronic cigarette users (and, for Italy, heat-not-burn cigarette users), and exposure to SHS and passive exposure to emissions from electronic cigarettes in selected European countries (WP3);
- to investigate the determinants of SHS exposure in those countries (WP3);
- to analyze the attitudes and perceptions of the adult European population towards policies to control tobacco and to limit SHS exposure (WP3);
- to study knowledge and beliefs of current smokers and the general adult population on the harmful effects of SHS (WP3);
- to compare smoking patterns, electronic cigarette use, and, particularly, SHS exposure between selected middle- and high-income countries in Europe (WP3);
- to compare smoking patterns, voluntary home smoking ban, and perception on the efficacy of smoking ban as a tobacco control policy between the new data in the selected European countries, and data from a companion pan-European survey conducted in 2010 (WP3);
- to assess: i) mortality attributable to SHS for lung cancer and ischaemic heart diseases among non-smoking adults; ii) morbidity (e.g., induction of asthma) attributable to SHS in non-smoking adults; iii) mortality attributable to SHS in children (e.g., Sudden Infant Death Syndrome [SIDS]); iv) morbidity (e.g., lower respiratory infections; asthma onset; acute otitis media) attributable to SHS in children (WP9);
- to quantify the economic burden associated to the exposure to SHS and e-cigarette aerosol in Europe (WP10).

METHODS

Study design

To achieve the aims of this study, we will conduct a face-to-face population-based cross-sectional survey in 12 strategically selected European countries (Bulgaria, England, France, Germany, Greece, Ireland, Italy, Latvia, Poland, Portugal, Romania, and Spain).

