The aforementioned statistical approaches will be used also to describe: i) the attitudes and perceptions of the adult European population towards policies to control tobacco and to limit SHS exposure; and ii) the knowledge and beliefs of current smokers and the general adult population on the harmful effects of SHS.

To evaluate the changes in time of selected smoking-related aspects, including smoking prevalence and patterns, voluntary home smoking ban, and perceptions on the efficacy of smoking bans as tobacco control policies, TackSHS data will be compared with data from a previous companion European survey (the PPACTE survey). A unique SAS dataset including common variables will be created for the 11 European countries considered in both surveys (i.e., BG, UK, FR, GR, IE, IT, LV, PL, PT, RO, and ES). Significance of differences between the two survey periods will be performed both through univariate (χ^2 test for categorical variables and t-test for continuous ones) and multivariate analysis (regression models).

Statistical analyses for WP9

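### The overall prevalence and attitude figures have no stated target and no country weights; as written they describe an average of 12 countries, not their combined population

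*Combined protocol and SAP*

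**What the plan says.** **Sample.** Study population: "In each of the 12 selected European countries, approximately 1000 individuals" are enrolled, about 12,000 in all. Sample size computation gives a maximum standard error below 1.6% per country and expects stable estimates ("with a relatively small 95% confidence interval), overall but also in each specific country").

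**Estimator.** The 12 country files are merged into one dataset. Statistical analyses for WP3 then estimates prevalence by univariate analysis ("i.e., descriptive statistics for categorical data, including absolute or relative frequencies), overall, by country, and in strata of selected demographic and socio-economic" characteristics). The same approaches are used to describe "the attitudes and perceptions of the adult European population towards policies to control tobacco and to limit SHS exposure".

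**Target.** The prevalence objective is looser. It covers smoking, e-cigarette use, exposure to secondhand smoke and "passive exposure to emissions from electronic cigarettes in selected European countries (WP3"). No section says whether an overall figure refers to the people of the 12 countries together, to the EU28, or to an equal average of countries.

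**Country size.** Selection of countries states that "the selection includes the 7 most populated EU MS (DE, ES, FR, IT, UK, PL, RO"), and that "the 12 selected EU MS represent 78.8% of the EU28 overall population". Data collection lists country population size among the country-level items, but nothing links it to a weight.

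**The concern.** Sample sizes are equal across countries and populations are not. Relative frequencies on the merged file therefore give a small country the same influence as a large one. The samples are meant to be representative within each country, but that does not settle how the countries are combined.

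An average-country figure and a combined-population figure are different quantities, and they coincide only if prevalence is unrelated to country size. The plan does not say which one it reports. For attitudes, the stated population is European adults, and plain frequencies do not estimate that. The overall interval will also be narrow because N is about 12,000, so a modest difference between the two quantities could exceed the reported uncertainty. A larger sample would not remove it.

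**Working it through.** **1. The plan's own figure.** Per-country SE at p = 0.5 and n = 1000: sqrt(0.25/1000) = 1.58 points, below the stated 1.6. Overall, by plain frequencies: sqrt(0.25/12,000) = 0.46 points, so the 95% half-width is 1.96 × 0.456 = 0.89 points. Both assume simple random sampling.

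**2. Country influence.** Each country: 1000/12,000 = 1/12 = 8.3%. The seven most populated: 7/12 = 58.3%. The other five (BG, GR, IE, LV, PT): 5/12 = 41.7%. In strata of individual characteristics such as age or education, a country counts by its respondents in that stratum rather than by 1/12, but still without regard to its population.

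**3. Direction of over-representation.** Let s be the five countries' share of the combined population. If the seven are the most populated EU states, with the UK as the unit, each of the five is smaller than each of the seven. Their mean share s/5 is then below the overall mean of 1/12, so s < 5/12. This follows from the protocol; the value of s does not.

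**4. Size of the difference.** Average-country minus combined-population figure = (5/12 − s) × (prevalence gap, five minus seven) + a remainder from unequal populations within each group. The first term, with s and the gap both assumed:

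| s | 10-point gap | 5-point gap | Gap at which the shift equals 0.89 |
|---|---|---|---|
| 7% | 3.47 | 1.73 | 2.6 |
| 10% | 3.17 | 1.58 | 2.8 |
| 15% | 2.67 | 1.33 | 3.4 |
| 20% | 2.17 | 1.08 | 4.1 |
| 30% | 1.17 | 0.58 | 7.7 |

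All entries except s are percentage points. Example: (0.4167 − 0.07) × 10 = 3.47; 0.895/(0.4167 − 0.07) = 2.6.

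**5. Precision cost of population weights.** SE = 1.58 × sqrt(sum of W_c²), where W_c is the country's population share. The Kish factor is 12 × sum of W_c².

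- s = 30%, equal shares within groups: sum = 0.30²/5 + 0.70²/7 = 0.088; SE 0.47; factor 1.06.
- s = 7%, equal shares within groups: sum = 0.07²/5 + 0.93²/7 = 0.1245; SE 0.56; factor 1.49.
- s = 7%, the seven spread linearly 1:4: sum = 0.1443; SE 0.60; factor 1.73.

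**6. Comparison with 2010.** The earlier survey averaged 18,056/18 = 1,003 per country, and the protocol says it used the same sample size. Each of the 11 shared countries therefore counts about 1/11 = 9.1% in both years. Country weights are already nearly the same at the two times, so only the label of that comparison is open.

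**The case against.** **The plan is silent rather than wrong.** Relative frequencies can be weighted, and country population size is to be collected. This stands: nothing excludes weights. But frequencies are the only estimator stated, and an analyst who follows the text produces the 1/12 average.

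**An equal-country average is a legitimate target.** This stands for prevalence, where the objective speaks only of selected European countries, provided the figure is labelled. It does not stand for attitudes, where the wording is European adults.

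**No population target was promised.** A reader might infer from the 78.8% coverage and the promise of stable overall estimates that the plan commits to a population prevalence. The documents do not support that. The first explains the choice of countries; the second concerns precision, and either average can meet it.

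**The size is illustrative.** This stands. Both inputs are assumed, and the half-width ignores clustering. At a 5-point gap the shift exceeds 0.89 only if s is below about 24%. With an assumed design effect of 2, the half-width grows by sqrt(2) and the break-even gaps become about 3.6 to 10.8 points. It is also tempting to set the gap against the 20% to 60% exposure range in Background and rationale. That range mixes surveys, some of them of single cities judging by their titles, and is not a gap between countries.

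**Weighting costs precision.** It does. At a Kish factor of 1.73, about 42% of the effective sample is lost (1 − 1/1.73). The overall SE nevertheless stays near 0.6 points.

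**Conclusion.** The point holds as a gap in the definition of the overall figures. As written, they are averages over countries in which the five less populated ones supply 41.7%, more than their population share. That does not match the population named for attitudes, and for prevalence it needs a label.

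The over-representation follows from the protocol's own statements. The resulting difference in prevalence does not: its size and sign are unknown. It is 3.5 to 1.2 points only under an assumed 10-point gap and an assumed share of 7% to 30%, and it is zero if prevalence is unrelated to country size. The countries were chosen partly for differing smoking prevalence, but nothing shows that prevalence follows population. A reader might conclude that the overall figures are biased by a known amount; the documents do not support that.

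By-country estimates do not change. The attributable-burden and economic work packages appear to use country-level inputs. Regression is not wholly outside the issue, because pooled odds ratios also average across countries by sample size. Their target should be stated, but this point requires no change to the models.

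**What to change.** Add to Statistical analyses for WP3:

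- **Weights.** Overall descriptive prevalence and attitude figures, and strata that span countries, are weighted to each country's population aged 15 and over, from a named source. Each respondent's weight is that population divided by the country's number of respondents, multiplied by any within-country design or post-stratification weight (scaled to mean 1). The last factor matters because Study design allows multistage, stratified and quota sampling.
- **Age range.** For attitudes, state the ages that adult covers and use the matching population. Minors are about 5% of the sample.
- **Variance.** Treat countries as strata. For the overall figure, SE = sqrt(sum of W_c² × SE_c²), with SE_c the country's design-based standard error.
- **England or the UK.** The protocol lists the country as England with the code UK; state which population is used.
- **Equal-country average.** Report it alongside, labelled as such.
- **Country clusters and 2010.** Label the target (average country or combined population) and use the same country weights in both years.
- **Regression.** State what population the pooled odds ratios describe.

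The cost is a short SAP addition and 12 population inputs. Country population size is already collected; the figure for ages 15 and over must be added. The nominal overall SE rises from 0.46 to about 0.47 to 0.60 points under the assumed shares.
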